## 4. Procedures and methods employed for analyzing the data

Analysis Plan. To test intervention effects under the Study Aim, we will use intention-to-treat analyses comparing intervention to control group outcomes. For inadequate healthcare engagement (<1 ambulatory visit, ≥1 emergency department visit, or ≥1 hospitalization in past 6 months) and receipt of evidence-based preventive care, we will conduct logistic regressions predicting whether participants had inadequate health care utilization or received evidence-based care within the entire follow-up period (yes/no). For coping, we will analyze all follow-up responses with repeated-measures linear regressions that include fixed effects for intervention condition, baseline value of the outcome, and covariates, employing a sandwich estimator to account for within-participant clustering; each participant can contribute up to three follow-up responses (from the 4-, 8-, or 12-month surveys).

Statistical Power. Based on our prior research, we anticipate medium effect sizes (0.5 SD). For analyses comparing intervention vs. control on continuous outcomes (e.g., coping) at follow-up, with a very conservative estimate of 240 participants (120 per group), there will be 80% power to

detect a difference of .36 SD (a small-to-medium effect size). For receipt of evidence-based preventive care, we used percentages from an analysis of our preliminary data, in which receipt of evidence-based care for CVD prevention and treatment ranged from 5.1% to 58.4% (and was lower for people living with HIV vs. people who were HIV-negative) [Ladapo JA, Richards AK, DeWitt CM, Harawa NT, Shoptaw S, Cunningham WE, Mafi JN. Disparities in the quality of cardiovascular care between HIV-infected versus HIV-uninfected adults in the United States: a cross-sectional study. J Am Heart Assoc. 2017;6(11):e007107. PubMed PMID: 29138182; PMCID: 5721786]. Thus, we estimated 80% power at 12-month follow-up to detect minimum between-groups difference representing small-to-medium effect sizes:

Control Group %	Minimum Detectable Difference	Effect Size (Cohn's D)
5%	11.0%	.37
30%	17.6%	.36
60%	16.8%	.36

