#### 2. How it will be done

A total of 370 Black participants will be recruited; approximately half will be randomly assigned to receive the coping intervention and half to a no-treatment control condition. There will be about 10 cohorts of about 15 participants each for both intervention and control. Participants will be randomized to an intervention or control group after they complete the baseline survey. Participants will complete four surveys, starting with the baseline survey, and followed by 4-, 8-, and 12-month post-baseline follow-up surveys to assess health care engagement and receipt of evidence-based preventive care (e.g., cancer and diabetes screening, cardiovascular disease prevention, immunization, HIV prevention), and other topics such as coping strategies.

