## 6. What study therapy or other interventions will be given?

The intervention is an 8-session CBT group intervention that addresses coping with discrimination and medical mistrust among Black SMM in order to improve health care utilization, receipt of evidence-based care, and overall health and wellness.

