## 2. Process of data selection for analyses

Data were selected for analysis in order to address study aims focused on evaluating the intervention in terms of primary and secondary outcomes as well as determining mediating mechanisms of change as well as moderators. (Due to premature study termination, only analyses with respect to primary and secondary outcomes will be conducted.)

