## 3. Detailed analyses of data items

Descriptive statistics will be performed on all study variables. We will transform any outcomes with skewed distributions (log or other as appropriate) to stabilize error variances and reduce the influence of outliers in regression models. To address potential bias from differential randomization and dropout, we will use covariates and non-response weights. Socio-demographic characteristics that significantly differ by intervention condition at will be included as covariates. Nonresponse weights will be used to address any potential differences between participants with complete data for at least one follow-up wave versus participants with only baseline data. Weights will be created using the inverse of the estimated probability of completing any follow-up survey, based on a multivariable logistic regression using socio-demographic and psychosocial variables that were not missing for any participant.

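### The treatment is given in CBT groups to one arm only, but no model accounts for group, so confidence intervals are too narrow if outcomes correlate within treated groups beyond what controls from the same wave share

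*Combined protocol and SAP*

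**What the plan says.** Protocol section 6: "The intervention is an 8-session CBT group intervention". Section 2 puts about "half to a no-treatment control condition". It adds "There will be about 10 cohorts of about 15 participants each for both intervention and control" and "Participants will be randomized to an intervention or control group after they complete the baseline survey". It does not say whether intervention and control cohorts come from the same recruitment waves.

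SAP section 4, both primary outcomes: "we will conduct logistic regressions predicting whether participants had inadequate health care utilization or received evidence-based care within the entire follow-up period". There is one yes/no value per participant, no term for group or cohort, and no clustered variance. For coping, the model is fitted by "employing a sandwich estimator to account for within-participant clustering; each participant can contribute up to three follow-up responses". That handles repeated surveys from one person, not people who share a group.

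SAP section 3 limits covariates to socio-demographic imbalances between arms and adds nonresponse weights: "Weights will be created using the inverse of the estimated probability of completing any follow-up survey". SAP section 6 adds timepoint-specific and longitudinal comparisons without a group term. No ICC or design effect appears anywhere. After early termination, SAP section 2 states that "only analyses with respect to primary and secondary outcomes will be conducted", so these are the models that will be reported.

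**The concern.** Men in one CBT group share sessions, facilitators and peers over eight meetings. Their later outcomes may be more alike than those of men in different groups. Controls have no therapy group, so any such correlation sits in one arm only. A model that treats all participants as independent then understates the variance of the treated-arm mean or proportion. The confidence intervals come out too narrow, and a nominal 5% test rejects too often. Both primary outcomes and the secondary outcome are affected. In a borderline result, a few well-functioning groups could not be told apart from an effect of the program.

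**Working it through.** **Inputs from the documents (SAP section 4, protocol section 2).** 120 analyzed per arm; 80% power at .36 SD; anticipated effect 0.5 SD; about 10 cohorts per arm.

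**Assumptions.** Two-sided 5% level (not stated). 10 treated groups of 12 analyzed (120/10). Excess ICC of .01, .02, .05 or .10 (none stated).

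**1. The plan's power figure.** (1.960 + 0.842) × √(2/120) = 0.362 SD, which is the stated .36. The three binary rows (5% + 11.0, 30% + 17.6, 60% + 16.8 points) give 79.8%, 80.3% and 80.3% power at 120 per arm. All of these match a design effect of 1, that is, independent participants.

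**2. Type I error of the planned test.** Let *g* be the ICC specific to treated groups and *w* the ICC of a wave effect shared by both arms. With groups of 12, the variance of the arm difference is (2 + 11*g* − 2*w*)/120, against the planned 2/120. So the true standard error is *f* = √((2 + 11*g* − 2*w*)/2) times the planned one, and type I error = 2 × (1 − Φ(1.96/*f*)).

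Example, ICC .05, all treated-only: *f* = √(2.55/2) = 1.129; 1.96/1.129 = 1.736; type I error 8.3%.

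| Total ICC | .01 | .02 | .05 | .10 |
|---|---|---|---|---|
| *f*, treated-only | 1.027 | 1.054 | 1.129 | 1.245 |
| Type I, treated-only | 5.6% | 6.3% | 8.3% | 11.5% |
| Type I, half shared by wave | 5.3% | 5.5% | 6.3% | 7.7% |
| Type I, all shared by wave | 4.9% | 4.8% | 4.4% | 3.9% |

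Standard errors are too small only when 11*g* > 2*w*. With *w* = .05, that means *g* above about .009.

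**3. Binary outcomes.** A simulated logistic test at a 30% event rate, treated-only, gives 5.5/6.3/8.5/11.4% when the ICC is on the observed 0/1 scale. When the ICC is on the latent logistic scale, it gives about 5.5/5.8/7.3/9.5%. The same nominal ICC is a weaker correlation on the 0/1 scale when it is defined on the latent one, so the scale must be named.

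**4. Cost of correcting, with the small-sample critical value.** Treated-only correlation, DE = 1 + 11 × ICC.
- Clustering on group, controls independent: Satterthwaite df = (1 + DE)² / (DE²/9 + 1/119).
- Clustering on wave: df = 10 − 1 = 9, t = 2.262.
- Widening = *f* × t/1.96 − 1. Power is from the noncentral t distribution.

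Example, ICC .05, group: df = 2.55²/(1.55²/9 + 1/119) = 23.6; t = 2.066; 1.129 × 2.066/1.96 = 1.19, so 19% wider.

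| ICC | 0 | .01 | .02 | .05 | .10 |
|---|---|---|---|---|---|
| Widening, group | 4% | 7% | 10% | 19% | 33% |
| Widening, wave | 15% | 18% | 22% | 30% | 44% |
| Power at .36 SD, group | 77% | 75% | 73% | 66% | 57% |
| Power at .36 SD, wave | 70% | 68% | 66% | 60% | 52% |
| Power at 0.5 SD, group | 96% | 95% | 94% | 91% | 84% |
| Power at 0.5 SD, wave | 93% | 92% | 90% | 86% | 79% |

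**The case against.** **Individual randomization after baseline.** This removes bias from how groups are formed. It does not remove correlation that arises afterwards from shared sessions.

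**Cohorts exist in both arms, so correlation may cancel.** This stands in part. The wording is compatible with shared waves, and wave-level correlation common to both arms does cancel; if that is all there is, the planned test errs slightly on the safe side. The documents do not say that waves are shared, and sharing would not cancel correlation arising inside the treated groups.

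**The ICC is unknown and may be small for healthcare use.** This stands. At .01 to .02 the excess is about one point or less, and only the upper part of the assumed range does material harm.

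**The cohort count is uncertain.** This also stands. 10 × 15 × 2 = 300, not 370, and the study ended early. The realised groups may differ from 10 of 12.

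**Stronger readings that a reader might infer.** One is that the planned tests are certainly anti-conservative. The documents do not support this, because neither the ICC nor the wave structure is given. Another is that the nonresponse weights will be used with model-based standard errors. The SAP states no variance method for the weighted logistic models, and silence is not a plan to use the wrong one. A third is that the trial is underpowered as a result. Power is secondary here because the study has already ended early, and at the anticipated 0.5 SD it remains 79% or more throughout the range above.

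**Conclusion.** The omission is clear in the text and applies to both primary outcomes and coping. Its consequence is conditional: intervals are too narrow if treated groups carry correlation beyond what controls in the same wave share. Its size rests on an assumed ICC and an assumed 10 groups of 12. Under those assumptions, true type I error lies between slightly below 5% (all correlation shared by wave) and about 11.5% (ICC .10, all treated-only). The stated 80% power at .36 SD holds only under independence. This is an inexpensive improvement that should be made before the final analysis; confidence is medium because the documents fix neither the ICC nor the cohort structure.

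**What to change.** First, state from trial records how cohorts were formed and how many groups, of what size, were realised. Then amend SAP section 4 for both primary outcomes and coping:

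- **No shared waves:** standard errors clustered on assigned CBT group, each control independent, with Satterthwaite-type degrees of freedom.
- **Shared waves:** cluster on wave, with t on the number of waves minus 1 degrees of freedom.
- Keep each participant in the assigned group regardless of attendance, in line with intention to treat. For coping, keep repeated surveys nested within participant.
- Choose the small-sample method to suit the realised number and size of groups. The cluster-robust variance also serves the weighted models of SAP section 3.

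**Cost.** SAP wording plus group and wave identifiers, which the documents do not mention and whose existence must be confirmed. No new outcome data are needed. Intervals widen and power falls as in the last table above, with some loss even at ICC 0. Clustering on group when all correlation is in fact shared by wave over-corrects: simulated rejection is 4.4/3.9/2.5/1.5% at ICC .01/.02/.05/.10. With about 10 groups, neither method is reliable near a 5% event rate (simulated null rejection 0.6 to 7.4%), so a result there needs a caveat.

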# 6. Plans for interim and final analysis and statistical analysis of the primary and secondary variables and other data

All analyses detailed above including timepoint specific follow-up as well as overall longitudinal models will compare intervention conditions on change in primary and secondary outcomes.

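### The two primary logistic models list no terms: adding the baseline value of the outcome, as the coping model already does, is a cheap gain in precision, not the repair of an error

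*Combined protocol and SAP*

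**What the plan says.** - **Primary outcomes (SAP section 4).** The plan states that "we will conduct logistic regressions predicting whether participants had inadequate health care utilization or received evidence-based care within the entire follow-up period". The arm term is implied by the comparison of groups; no other term is given.
- **Coping, the secondary outcome (same paragraph).** The repeated-measures model has "fixed effects for intervention condition, baseline value of the outcome, and covariates".
- **Covariates in general (SAP section 3).** "To address potential bias from differential randomization and dropout, we will use covariates and non-response weights". This is not tied to one outcome, so it plausibly reaches the logistic models. The only selection rule that follows is "Socio-demographic characteristics that significantly differ by intervention condition at will be included as covariates".
- **Change (SAP section 6).** All analyses, timepoint-specific and longitudinal, "will compare intervention conditions on change in primary and secondary outcomes". No model of change is given for a yes/no outcome.
- **Availability of a baseline value.** Protocol section 2 says "Participants will be randomized to an intervention or control group after they complete the baseline survey". Protocol section 8 has both primary outcomes assessed from baseline onward.

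**The concern.** The secondary outcome is specified more fully than either primary. Followed as written, the primary models would leave out a pre-randomization measurement that the trial already collects. Baseline utilization and baseline receipt of care are not socio-demographic, so the SAP section 3 rule would not admit them even if they were badly imbalanced. That rule also selects on chance differences between arms rather than on prognostic value.

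The reference to change in SAP section 6 may signal that a baseline term is intended, but it does not say how. An arm-only model and a baseline-adjusted model both fit the text. The choice affects the precision of the primary comparison and the meaning of the reported odds ratio.

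**Working it through.** **Inputs.** From SAP section 4: 120 per group; 0.36 SD for continuous outcomes; control rates of 5%, 30% and 60% with differences of 11.0, 17.6 and 16.8 points; 80% power; anticipated effect 0.5 SD. From Protocol section 2: 370 recruited, about half per arm, so 370/2 = 185. Assumed because not stated: two-sided 5% test, and every baseline-to-follow-up correlation.

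**Step 1: the plan's own power, with no baseline term.**

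Continuous: z = 0.36/√(2/120) − 1.96 = 2.789 − 1.960 = 0.829, power 79.6%.

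Binary: z = [d√n − 1.96√(2p̄q̄)] / √(p₁q₁ + p₂q₂), with p̄ the mean of the two rates.
- 5% vs 16.0%: (1.205 − 0.850)/0.4265 = 0.833, power 79.8%.
- 30% vs 47.6%: (1.928 − 1.351)/0.6778 = 0.852, power 80.3%.
- 60% vs 76.8%: (1.840 − 1.289)/0.6467 = 0.853, power 80.3%.

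The stated 80% reproduces as an unadjusted comparison.

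**Step 2: add a binary baseline status.** Simulated logistic models (arm only; arm plus baseline), Wald test, 120 per arm, latent correlation 0.2, 0.5 and 0.7, baseline prevalence equal to the control rate, 100,000 replicates per cell. Observations are independent and unweighted, so group delivery and non-response weights are ignored.

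| Row | Assumed phi | Power without → with baseline |
|---|---|---|
| 5% vs 16% | 0.06, 0.20, 0.36 | .802→.800, .805→.817, .803→.845 |
| 30% vs 47.6% | 0.12, 0.32, 0.48 | .808→.807, .806→.841, .809→.889 |
| 60% vs 76.8% | 0.13, 0.33, 0.49 | .803→.809, .804→.845, .804→.891 |

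The gain is about 0 to 9 points in the 30% and 60% rows and about 0 to 4 in the 5% row. At phi of about 0.7 the 30% and 60% rows would gain about 16 points, but nothing in the documents supports so strong a link.

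**Step 3: mismatched windows.** If only 10% are positive at baseline against 30% at control follow-up (assumed), phi of 0.10, 0.26 and 0.38 gives .810→.807, .811→.825 and .809→.852 (20,000 replicates): about 0 to 4 points.

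**Step 4: more favourable conditions** (30% control rate, same latent correlations, 3,000 replicates).
- Anticipated 0.5 SD, read as an arcsine difference of 0.5, 120 per arm: about .975→.977, .981, .995, a gain of about 0 to 2 points.
- +17.6 points, 185 per arm: .944→.948, .941→.959, .933→.975, a gain from under 1 point to about 4.

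**Step 5: type I error.** Over all randomizations it is .049 to .050 with or without the baseline term (400,000 replicates).

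**Step 6: what the odds ratio means.** In the 30% row the marginal odds ratio is (.476/.524)/(.30/.70) = 2.12. The conditional odds ratio for the same risks is 2.29 at phi 0.3 and 2.70 at phi 0.5. In the 60% row, 2.21 becomes 2.37 and 2.78.

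**Step 7: sparsity at 5%.** Baseline positives: 240 × 0.05 = 12. Follow-up positives: 120 × 0.05 + 120 × 0.16 = 25.2. In simulation, separation or no control event among baseline-negative men occurred in about 11%, 3% and 3% of datasets at latent correlation 0.2, 0.5 and 0.7, and in about 20% at 0.9. At 0.9 the Wald test had power .824 and the likelihood-ratio test .939.

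**The case against.** The best defence is that an unadjusted randomized comparison is valid, the power statement assumes nothing else, and the general covariate sentence and the reference to change may already intend a baseline term. All of that stands, which is why this is an improvement and not an error.

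The size is also open to challenge, and most of the challenge holds. The larger gains arise at the minimum detectable difference and at a sample size that the plan itself calls very conservative. The three control rates come from cardiovascular care, whereas the primary measure is all-or-none across several categories and so may be rarer; the 5% row may then be the closest. No rate is given for inadequate utilization. The baseline link may be weak: utilization has a 6-month look-back, evidence-based care has no stated one, and the models score the whole follow-up period.

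Two stronger readings are tempting.

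- **That the primary test has inflated type I error.** With 30% prevalence and no true effect, baseline status differs by 10 points or more in 10.5% of randomizations at 120 per arm and 3.6% at 185. Within those, the unadjusted error rate at phi 0.48 is about 13.5% and 18.8%. These figures come from selecting the worst randomizations; the others fall below 5% and the average is 5%. They do not show a defect in the test.
- **That the sponsor decided to leave baseline out.** The text is silent on the terms; it does not record such a decision.

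HIV status is a tempting mandatory covariate because SAP section 4 says that receipt of care "was lower for people living with HIV vs. people who were HIV-negative". That statement concerns cardiovascular care only, and HIV status partly determines which services count in the composite.

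**Conclusion.** The plan would be better with the baseline value of the outcome in both primary models, and the present covariate rule would not put it there. The benefit is precision: at 120 per arm and the minimum detectable difference, about 0 to 9 points of power in the 30% and 60% rows for phi of about 0.1 to 0.5, and about 0 to 4 points if the outcome is near 5% or the baseline window captures fewer positives. It falls to at most about 4 points at 185 per arm and about 2 at the anticipated effect. Every correlation is assumed, so these ranges illustrate and do not bound the gain. No stated figure is wrong and no bias is shown.

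**What to change.** - **SAP section 4.** State that both primary logistic models include intervention condition and the baseline value of the same outcome, whatever the observed balance. Define the baseline look-back window and the services counted as eligible at baseline. Name a fallback for sparse cells (penalized likelihood or a likelihood-ratio test). Report a standardized (marginal) risk difference or odds ratio beside the conditional odds ratio.
- **SAP section 3.** Replace selection by significant arm difference with a short covariate set fixed before outcome data are examined. Do not mandate HIV status.
- **SAP section 6.** Define change for the binary outcomes, including the timepoint-specific analyses, as follow-up status adjusted for baseline status.

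**Cost.** A few sentences and no new data. The adjusted odds ratio becomes conditional, the baseline look-back may not match the whole follow-up period, and additional covariates should be few if the outcome is rare. The study ended early (Protocol section 8, SAP section 2); if analysis has already begun, the adjusted model must be labelled post hoc.

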## 5. Who is eligible to take part in it?

Eligibility criteria include: 18 years of age or older; Biologically male at birth; Identify as male; Self-identify as a Black/African American; Report having sex with men in the past 24 months; Anticipate being available for the next 12 months to attend study visits; Able to interact and communicate in written and spoken English.

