#### 8. What information will be collected

- 1. From baseline to 12-month post-baseline we will assess the Primary Outcome Measure: Proportion of Participants Who Have Inadequate Healthcare Utilization (self-reported). The survey will assess number of medical care visits in different settings (usual source of medical care, primary care visits, missed visits, urgent care, emergency department, hospital inpatient, residential care facility, hospital outpatient clinic, other type of clinic, dental care provider, home healthcare). We will construct measures of inadequate service utilization as having: (1) fewer than 1 ambulatory visit, (2) at least 1 emergency department visit (without subsequent hospitalization), or (3) at least 1 hospitalization in the past 6 months. Higher numbers of hospital visits and emergency department use likely results from not receiving indicated outpatient treatment, which can prevent complications, even among those who experience multiple chronic conditions.
- 2. From baseline to 12-month post-baseline we will assess the Primary Outcome Measure: Proportion of Participants Receiving Evidence-based Care Across Conditions and Assessments (self-reported). We will calculate receipt of evidence-based care as receipt of all eligible services within health condition categories (cancer screening, CVD prevention, immunization, diabetes care, HIV prevention, HIV treatment), and create an "all-or-none" measure across all categories.
- 3. From baseline to 4 months, to 8 months, and to 12 months, we will measure change the Secondary Outcome Measure, Adaptive Coping Strategies (Social Support Seeking; e.g., "I get emotional support from others"). Relevant items on the Brief Cope a general measure of coping strategies, will be adapted to assess frequency of use of each strategy, using the instructions, "indicate the extent you do what the item says when you are faced with discrimination," and response options 1 = "I haven't been doing this at all," 2 = "I've been doing this a little bit," 3 = "I've been doing this a medium amount" and 4 = "I've been doing this a lot."

Note: The study team originally planned to validate self-reported health care behaviors and outcomes with medical records data, but the grant was terminated before the team could collect these objective data.

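### HIV status helps define the evidence-based-care primary and is probably prognostic for it, but the SAP's covariate rule would not put it in the model; prespecify it as a covariate.

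*Combined protocol and SAP*

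**What the plan says.** - **Eligibility (Protocol section 5).** The criteria include "Report having sex with men in the past 24 months" but nothing on HIV status, so men with and without HIV can both enter.
- **Endpoint (Protocol section 8, item 2).** The primary is scored as "receipt of all eligible services within health condition categories (cancer screening, CVD prevention, immunization, diabetes care, HIV prevention, HIV treatment", then combined into one all-or-none result. HIV prevention and HIV treatment are separate categories.
- **Power rationale (SAP section 4).** In the preliminary data, "receipt of evidence-based care for CVD prevention and treatment ranged from 5.1% to 58.4" percent, and receipt "was lower for people living with HIV vs. people who were HIV-negative". The size of the HIV difference is not given.
- **Randomization (Protocol section 2).** "Participants will be randomized to an intervention or control group after they complete the baseline survey". Allocation is about 1:1. No method and no stratification factor is described.
- **Covariates (SAP section 3).** "Socio-demographic characteristics that significantly differ by intervention condition at will be included as covariates". A word seems to be missing after "at"; I read it as baseline. The nonresponse weights draw on socio-demographic and psychosocial variables.
- **Models (SAP section 4).** The sentence on the two primary logistic regressions names no covariate. Only the coping model is given a baseline value and covariates.

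No section makes HIV status a covariate.

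**The concern.** A covariate earns its place in a randomized comparison by predicting the outcome. A significant difference between arms at baseline is a poor reason to include one: it misses strong predictors with moderate imbalance, admits weak ones that differ by chance, and leaves the final model unknown until the data are seen.

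HIV status is a clear case here. It helps determine which services count towards success, and the sponsor's own preliminary data show an HIV difference in one of the component categories. It is a health characteristic, so the stated rule does not reach it. If the team did class it as socio-demographic, it would enter only after a significant imbalance.

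At stake is a modest amount of precision on one of the two primaries, and a result that would be harder to interpret if the arms happened to differ in HIV share.

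**Working it through.** **Inputs from the documents (SAP section 4).** 120 per group; 80% power; detectable differences of 11.0, 17.6 and 16.8 points over control rates of 5%, 30% and 60%.

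**Assumptions, not in the documents.** Two-sided alpha 0.05; simple 1:1 randomization; HIV share q of 20-40%; gap g in the success rate between men with and without HIV of 5-30 points.

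**1. The plan's own figures.** The usual two-proportion normal approximation, with no continuity correction and no covariate, gives power of 79.8%, 80.3% and 80.3% at 120 per group. The table is reproduced, and nothing below changes the sample size or the detectable differences.

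**2. How large an imbalance in HIV share can pass as non-significant.** The limit is 1.96 × √[2q(1−q)/n].
- n = 120, q = 0.2: 1.96 × 0.0516 = 10.1 points. q = 0.4: 1.96 × 0.0632 = 12.4 points.
- n = 185 (half of 370): 8.2 and 10.0 points.

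So even if HIV status were classed as socio-demographic, at 120 per arm it would enter only when the arms differed by about 10 to 12 points or more.

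**3. Shift in the arm difference at that limit.** Shift = imbalance × g, at n = 120.

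| Gap g | q = 0.2 | q = 0.4 |
|---|---|---|
| 10 points | 1.0 | 1.2 |
| 20 points | 2.0 | 2.5 |
| 30 points | 3.0 | 3.7 |

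At n = 185, gaps of 20-30 points give 1.6 to 3.0 points. These are 95% limits. A one-standard-deviation imbalance at n = 120 gives 1.0 points (5.16 × 0.20) to 1.9 points (6.32 × 0.30).

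**4. Power gained by adjusting.** On a linear approximation, HIV status explains R² = q(1−q)g² / [p(1−p)] of the outcome variance, with p the control rate. If b is the unadjusted power quantile plus 1.96, adjusted power is Φ(b/√(1−R²) − 1.96). Example: p = 0.30, q = 0.4, g = 0.30 gives R² = 0.24 × 0.09 / 0.21 = 0.103. With b = 2.812, power is Φ(2.812/0.947 − 1.96) = 84.3%.

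Over q = 20-40% and p = 30% or 60%, starting from 80.3%:

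| Gap g | Adjusted power | Gain |
|---|---|---|
| 5-10 points | 80.4-80.7% | under 1 point |
| 20 points | 81.4-82.1% | 1.0-1.8 points |
| 30 points | 82.7-84.3% | 2.4-4.1 points |

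**5. Control rate near 5%.** If men with HIV do worse, the gap cannot exceed p/(1−q), because their rate cannot fall below zero: 0.05/0.8 = 6.3 points at q = 0.2 and 0.05/0.6 = 8.3 points at q = 0.4. The 95% shift is then at most 10.1 × 0.063 = 0.6 to 12.4 × 0.083 = 1.0 points. The power gain at those maximum gaps is 0.5 to 1.4 points, from 79.8%.

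**The case against.** **The HIV difference is quoted for one component only.** This stands. SAP section 4 reports it for cardiovascular prevention and treatment, in preliminary data, without a size. The other categories could widen, cancel or reverse it. That HIV status is prognostic for the composite is a reasonable expectation, resting mainly on how the endpoint is scored; the documents do not demonstrate it.

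**A reader might infer that the unadjusted analysis is biased.** It is not. Randomization keeps it unbiased on average, and its standard error already allows for chance imbalance in prognostic factors. At 120 per arm the 95% half-width is 1.96 × √(2 × 0.3 × 0.7/120) = 11.6 points at a 30% rate and 12.4 points at 60%. The shifts in step 3 are part of that uncertainty.

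**A reader might infer that the rule forbids HIV status.** SAP section 3 says in general that covariates will be used, then names one class of them. It does not expressly bar others. The fair statement is that HIV status is not covered by the rule as written.

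**A reader might ask for stratified randomization.** Protocol section 2 is silent on the method, which does not show that stratification was absent. The documents also report early termination, so the request is probably moot.

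**A reader might ask for separate effects by HIV status.** SAP section 2 discloses that, after termination, only primary and secondary outcome analyses will be run. At an HIV share of 20-40% there would be 24 to 48 men with HIV per arm (0.2 × 120 to 0.4 × 120). With a 30% control rate, the detectable difference in that group would be about 28 to 39 points, too large to be informative.

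**A reader might extend the point to both primaries.** Nothing in the documents links HIV status to inadequate utilization.

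**Conclusion.** The point holds as a low-cost improvement to the evidence-based-care analysis. HIV status is likely to matter for that endpoint because it helps determine which services are required, and the covariate rule would leave it out or make its entry depend on a significance test.

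The size depends on two quantities the documents do not give. With an HIV share of 20-40% and control rates of 30% or 60%, a gap of 5-10 points makes the gain negligible. A gap of 20-30 points makes it about 1 to 4 points of power, with a chance shift of up to about 2 to 4 points at the 95% limit, against detectable differences of 16.8-17.6 points at those control rates. Near a 5% control rate the shift is about 1 point or less.

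The documents do not support reading this as an invalid test, a wrong sample size, a failure to stratify, or evidence that HIV status predicts utilization.

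**What to change.** In SAP section 3, state that baseline HIV status is a prespecified covariate for the evidence-based-care primary, included whether or not it differs between arms. In SAP section 4, name it in the logistic model for that outcome, and note that the adjusted odds ratio is conditional on HIV status and so differs in meaning from an unadjusted one. Make the change before the outcome data are analysed by arm.

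The cost is a sentence in each section and one degree of freedom. No new data should be needed, because assigning the HIV prevention or HIV treatment category already requires HIV status. The sample size is unaffected.
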